5.5 RESPONSE ASSESSMENT RE-TREATMENT

Tumor assessment will be performed cycles 7, 14, 20 and 26 then every 12 months. Best clinical response and disease progression will be investigator assessed.

5.6 DISCONTINUATION FROM STUDY

Subjects will be discontinued from the study for any of the following reasons:

- Disease progression while on study treatment
- Disease progression within 6 months during treatment-free observation
- Subject requests to withdraw consent or discontinue treatment
- Pregnancy
- Inability of the subject to comply with study requirements
- Conditions requiring therapeutic intervention not permitted by the protocol
- Non-compliance/lost to follow-up
- Investigator discretion
- Discontinuation of the study by the Sponsor

Subjects who discontinue from study treatment (for reasons other than progressive disease) will continue to be followed for progression and survival for 24 months.

After withdrawal from study, subjects should be followed for AEs for 30 calendar days after their last dose of either study drug. All new AEs occurring during this period must be reported and followed until resolution, unless, in the opinion of the investigator, these values are not likely to improve because of the underlying disease. In this case the investigators must record his or her reasoning for this decision in the subject's medical records and as a comment on the electronic Case Report Form (eCRF).

5.7 STUDY SITES

Up to eight centers in the United States may be asked to participate in this study. Enrollment is expected to be completed approximately 24 months after the first subject is enrolled.

6 REGISTRATION AND ENROLLMENT

Subjects who are eligible and have signed an informed consent will add ublituximab and umbralisib to their existing ibrutinib, acalabrutinib or venetoclax treatment. Determination of which cohort each subject will be enrolled in will depend on which agent was received prior to screening.

Three Cohorts will be studied:

- Cohort A: Ublituximab and Umbralisib with Ibrutinib
- Cohort B: Ublituximab and Umbralisib with Venetoclax
- Cohort C: Ublituximab and Umbralisib with Acalabrutinib

After the subject signs the informed consent form and to register the subject, the completed Subject registration form will be emailed to [contact].

After eligibility has been confirmed, subject enrollment forms with the signed inclusion/exclusion form will be emailed to [contact].

If the subject is a screen failure, the site must notify TG Therapeutics by email at [contact].

If subject is eligible to enter the Re-Treatment phase, the completed Subject Re-Treatment Registration form will be emailed to [contact].

7 STUDY ASSESSMENTS AND TREATMENT SCHEDULES

7.1 STUDY ASSESSMENT AND TREATMENT SCHEDULE - INITIAL TREATMENT

Cycle=28 days	Screen	Cycle 1 ¹				Cycle 2-6 ²	C9 and every 3 cycles through C24 ³	EOS*
Procedure/Days	-28-1	D1	D2	D8	D15	Day 1	Day 1	
Medical History	X							
Rai Staging	X							
ECOG	X	X				X	X	X
Physical Examination	X	X				X	X	X
Vital Signs⁴	X	X	X	X	X	X	X	X
12-Lead EKG	X							
Hematology	X	X	X	X	X	X	X	X
Chemistry	X	X	X	X	X	X	X	
Coagulation Studies	X	X				X	X	
HCV, HBV, CMV⁵	X							
CMV surveillance⁶						C3&6	C9, 12, 15, etc.	
PB MRD⁷	X					X	X	
β₂-microglobulin	X							
Pregnancy Test⁸	X					X	X	
Response assessments¹⁰	X					C3 & C6	C 12, 18 & C24	
AE Evaluation	X	X	X	X	X	X	X	X
Con Meds	X	X	X	X	X	X	X	X
Ublituximab		X	X	X	X	X	X	
Umbralisib						Daily until confirmed U-MRD ¹¹		
Cohort A: Ibrutinib						Daily until confirmed U-MRD ¹¹		
Cohort B: Venetoclax						Daily until confirmed U-MRD ¹¹		
Cohort C: Acalabrutinib						Every 12 hours until confirmed U-MRD ¹¹		

¹ Treatment Administration +/- 1 day window after cycle 1 day 1. Physical Exam, Vital Signs, ECOG PS, Hematology and Serum Chemistry visit days have - 1 day window. All assessments must be completed prior to dosing.

² Treatment Administration +/- 3 day window. Physical Exam, Vital Signs, ECOG PS, Hematology and Serum Chemistry visit days have a - 3 day window during Cycles 2 through 6.

³ Treatment Administration +/- 7 day window. Physical Exam, Vital Signs, ECOG PS, Hematology and Serum Chemistry visit days have a - 7 day window for all cycles after cycle 6

⁴ Vital signs to include temp, BP, HR, respirations and weight (weight only at baseline).

⁵ Serum Virology to include HBsAg, HBc antibody, HCV antibody, CMV IgG and IgM. If HBc antibody is positive, the subject must be evaluated for the presence of HBV DNA by PCR - See Appendix D. If the subject is CMV IgG or IgM positive, the subject must be evaluated for the presence of CMV DNA by PCR. If subject is HCV positive, evaluate HCV RNA.

⁶ CMV surveillance by PCR every 3 cycles while receiving study treatment. In addition, a final CMV test by PCR should be done upon treatment discontinuation if not already done within previous 3 months.

⁷ For initial treatment, MRD analysis (central lab) in peripheral blood (PB) performed within 30 days prior to Cycle 1/Day 1. MRD analysis in PB during cycles 3, 6, 9, 12, 15, 18, 21, and 24. U-MRD in PB during initial treatment must be confirmed in PB 4 approximately weeks later.

⁸ For women of childbearing potential: Serum pregnancy test within 3 days prior to Cycle 1/Day 1; Urine pregnancy tests on Day 1 of each treatment cycle +/- 7 days.

¹⁰ Radiology assessment should include a contrasted CT or MRI imaging of neck, chest, abdomen, and pelvis. For initial treatment, scans to be completed within 30 days prior to Cycle 1 / Day 1. All tumor evaluations post baseline assessment should be performed within 14 days of cycles 3, 6, 12, 18 and 24.. Follow up CTs to be done at investigator discretion/ per standard of care. At the time of response assessment, bone marrow to be performed as per standard of care if other criteria for complete remission are met. CR should only be confirmed once by bone marrow assessment at planned tumor assessments.

¹¹ If U-MRD is confirmed, subjects will complete treatment through the end of that 28-day cycle then return for their first TFO at the subsequent Cycle.

***EOS = End of Study** – EOS visit occurs if subject is discontinuing from the study. Please see Section 5.6 Discontinuation from study , which outlines reasons subject must discontinue from study.

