---------------------------	--

[figure not shown]
	
8. Willingness and ability to comply with trial and follow-up procedures and give written informed consent.

Exclusion Criteria
	
1. Subjects receiving cancer therapy (i.e., chemotherapy, radiation therapy [excluding palliative radiation to areas not including target/non-target lesion(s)], immunotherapy, biologic therapy, hormonal therapy, surgery and/or tumor embolization) or any investigational drug within 21 days of Cycle 1/Day 1. This does not include ibrutinib, acalabrutinib or venetoclax but does include anti-CD20 therapy.
 
 a. Corticosteroid therapy started at least 7 days prior to Cycle 1/Day 1 (prednisone \leq10 mg daily or equivalent) is allowed as clinically warranted. Topical or inhaled corticosteroids are permitted. 
2. Evidence of chronic active Hepatitis B (HBV, not including subjects with prior hepatitis B vaccination; or positive surface Hepatitis B antibody) or chronic active Hepatitis C infection (HCV), cytomegalovirus (CMV), or known history of HIV. Subjects with positive HBc antibody or HCV antibody are eligible only if PCR is negative for HBV DNA or HCV RNA.
 
3. Known histological transformation from CLL to an aggressive lymphoma (i.e. Richter's transformation).
 
4. Evidence of ongoing systemic bacterial, fungal or viral infection, except localized fungal infections of skin or nails. NOTE: Subjects may be receiving prophylactic antiviral or antibacterial therapies at investigator discretion. Use of anti-pneumocystis and antiviral prophylaxis is required for subjects on umbralisib.
 
5. Live virus vaccines within 4 weeks prior to ublituximab therapy.
 
6. History of anaphylaxis in association with previous anti-CD20 administration.
 
7. For subjects receiving ibrutinib or acalabrutinib:
 
 a. Subjects requiring warfarin therapy. b. Subjects requiring strong CYP3A inhibitors and/or inducers 
8. For subjects receiving venetoclax:
 
 a. Requirement for use of strong or moderate CYP3A inhibitors, strong or moderate CYP3A inducers, P-gp inhibitors, or narrow therapeutic index P-gp substrates. 
9. Any severe and/or uncontrolled medical conditions or other conditions that could affect their participation in the study such as:
 
 a. Symptomatic, or history of documented congestive heart failure (NY Heart Association functional classification III-IV) b. Myocardial infarction within 6 months of enrollment

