Following screening, qualified subjects will add ublituximab and umbralisib to their existing ibrutinib, acalabrutinib or venetoclax treatment. Any therapy previously given concurrently with ibrutinib, acalabrutinib or venetoclax, including anti-CD20 therapy, must have been discontinued 21 days prior to Day 1 of Cycle 1 (See Exclusion Criterion #1). Determination of enrollment in Cohort A versus Cohort B or Cohort C will depend on which agent the subject was receiving prior to screening (ibrutinib, acalabrutinib or venetoclax).

Three cohorts will be studied:

- **Cohort A:** ublituximab and umbralisib with ibrutinib
- **Cohort B:** ublituximab and umbralisib with venetoclax
- **Cohort C:** ublituximab and umbralisib with acalabrutinib

Up to approximately 28 subjects may be enrolled into each cohort.

Study Duration

MRD status of all subjects will be evaluated during cycles 3, 6, 9, 12, 15, 18, 21, and 24. If subjects achieve U-MRD status in the peripheral blood, MRD will again be assessed by peripheral blood 4 weeks later to confirm U-MRD. Subjects will remain on study treatment through 24 cycles or the occurrence of confirmed U-MRD response in the peripheral blood, after which they will enter a period of treatment-free observation.

Following achievement of U-MRD, subjects will enter a period of treatment-free observation (TFO) with serial MRD assessments every 12 weeks up to Cycle 24 then every 24 weeks thereafter, unless clinically indicated sooner.

Subjects who do not achieve confirmed U-MRD will continue treatment until the completion of 24 cycles of treatment, definitive disease

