2.2.2.1 PHARMACOKINETICS

After infusion of ublituximab (previously known as LFB-R603) at a 150 mg dose followed by seven weekly injection infusions at 450 mg, results suggested non-linear pharmacokinetics with respect to dose (450 mg vs. 150 mg) and time (week 4 vs. week 8) and more than proportional increase of C_{max} and AUC_∞ due to a clearance decrease. The volume of distribution at steady state was small (~5 L), approximately equal to blood volume. These non-linear pharmacokinetics may be explained by binding of ublituximab to its target, with a large component of target-mediated elimination after the first dose that is decreased after subsequent infusions due to a reduction in the available target. However, limited data for each dose level cohort and considerable variability in baseline patient characteristics, particularly in terms of tumor burden, make firm conclusions difficult.

The linear mean serum concentration-times profile after the first, the fourth and the eighth infusion of ublituximab are presented in Figure 1. A summary of non-compartmental PK parameters after the first, the fourth and the eighth infusion of ublituximab are presented in Table 1.

FIGURE 1: LINEAR MEAN SERUM CONCENTRATION-TIMES PROFILE AFTER THE FIRST, THE FOURTH AND THE EIGHTH INFUSION OF UBLITUXIMAB

[figure not shown]

TABLE 1: PHARMACOKINETIC RESULTS AFTER THE 1ST (150 MG), THE 4TH (450 MG) AND THE 8TH (450 MG) INFUSION OF UBLITUXIMAB

PK Parameters ^a	1 st Infusion 150 mg (Day 1)	4 th Infusion 450mg (Day 22)	8 th Infusion 450 mg (Day 50)
N	12	11	11
C _{max} (mg/L)	23.4 ± 11.2	168.6 ± 61.8	220.5 ± 141.9
t _{max} (h)	9.0 (5.0-30.3)	5.00 (3.1-52.0)	5.1 (3.1-23.5)
AUC _∞ (mg.h/L)	732.1 ± 590	17890 ± 17730*	50760 ± 74460
t _{1/2term} (h)	13.43± 10.2	80.7 ± 58.5*	147.8 ± 133.8
CL (mL/h)	424.2 ± 389.3	57.69 ± 42.91	38.62 ± 26.63
V _d /V _{dss} (L)	4.8 ± 2.1	4.9 ± 2.3*	5.7 ± 3.3

^a mean ± SD, t_{max}: median (range), with respect to the start of infusion

*Accurate determination not possible

Concentration was still measurable in at least one patient of the cohort up to day 169. Values for C_{max} and AUC_∞ increased from the first to the eighth infusion whereas t_{1/2} term decreased.

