4.1 INCLUSION CRITERIA

1. Subjects with CLL who are currently receiving treatment with ibrutinib, acalabrutinib or venetoclax for greater than or equal to 6 months.
2. Minimal residual disease (MRD) positive (D-MRD) as determined by central lab performed during screening period.
 - a. For subjects receiving venetoclax: response assessment demonstrating stable disease, partial response, or complete response AND detectable MRD in the peripheral blood (central lab).
 - b. For subjects receiving ibrutinib or acalabrutinib: response assessment demonstrating stable disease, partial response or partial response with lymphocytosis, or complete response AND detectable MRD in the peripheral blood (central lab).
3. Adequate organ system function, defined as follows:
 - a. Absolute neutrophil count (ANC) $\geq 1,000/\text{mm}^3$ (μL) / platelet count $\geq 50,000/\text{mm}^3$ (μL). Growth factor to maintain these counts is permitted during screening period and throughout the conduct of the trial.
 - b. Total bilirubin ≤ 1.5 times the upper limit of normal (ULN), unless a diagnosis of Gilbert's syndrome or an autoimmune hemolytic anemia.
 - c. Alanine aminotransferase (ALT) and aspartate aminotransferase (AST) $\leq 2.5 \times \text{ULN}$ if no liver involvement or $\leq 5 \times \text{the ULN}$ if known liver involvement.
 - d. Calculated creatinine clearance $>30 \text{ mL/min}$ (as calculated by the modified Cockcroft-Gault formula, MDRD formula, or 24-hour urine CrCl).
4. ECOG performance status ≤ 2 .
5. Male or female ≥ 18 years of age.
6. Ability to swallow and retain oral medication.
7. Female subjects who are not of child-bearing potential (see Appendix B- Contraceptive Guidelines and Pregnancy), and female subjects of child-bearing potential who have a negative serum pregnancy test within 3 days prior to Cycle 1, Day 1. Female subjects of child-bearing potential, and male partners must consent to use a medically acceptable method of contraception throughout the study period and for 4 months after the last dose of ublituximab or umbralisib, and for at least 30 days after the last dose of ibrutinib, acalabrutinib or venetoclax.
8. Willingness and ability to comply with trial and follow-up procedures and give written informed consent.

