4.2 EXCLUSION CRITERIA

1. Subjects receiving cancer therapy (i.e., chemotherapy, radiation therapy [excluding palliative radiation to areas not including target/non-target lesion(s)], immunotherapy, biologic therapy, hormonal therapy, surgery and/or tumor embolization) or any investigational drug within 21 days of Cycle 1/Day. This does not include ibrutinib, acalabrutinib or venetoclax but does include anti-CD20 therapy.
 - a. Corticosteroid therapy started at least 7 days prior to Cycle 1/Day 1 (prednisone ≤10 mg daily or equivalent) is allowed as clinically warranted. Topical or inhaled corticosteroids are permitted.
2. Evidence of chronic active Hepatitis B (HBV, not including subjects with prior hepatitis B vaccination; or positive surface Hepatitis B antibody) or chronic active Hepatitis C infection (HCV) cytomegalovirus (CMV), or known history of HIV. Subjects with positive HBc antibody or HCV antibody are eligible only if PCR is negative for HBV DNA or HCV RNA. Antiviral prophylaxis for HBV reactivation should be considered for HBc antibody positive subjects at investigator discretion.
3. Known histological transformation from CLL to an aggressive lymphoma (i.e. Richter's transformation).
4. Evidence of ongoing systemic bacterial, fungal or viral infection, except localized fungal infections of skin or nails. NOTE: Subjects may be receiving prophylactic antiviral or antibacterial therapies at investigator discretion. Use of anti-pneumocystis and antiviral prophylaxis is required for subjects on umbralisib.
5. Live virus vaccines within 4 weeks prior to ublituximab therapy.
6. History of anaphylaxis in association with previous anti-CD20 administration.
7. For subjects receiving ibrutinib or acalabrutinib:
 - a. Subjects requiring warfarin therapy.
 - b. Subjects requiring strong CYP3A inhibitors and/or inducers.
8. For subjects receiving venetoclax:
 - a. Requirement for use of strong or moderate CYP3A inhibitors, strong or moderate CYP3A inducers, P-gp inhibitors, or narrow therapeutic index P-gp substrates.
9. Any severe and/or uncontrolled medical conditions or other conditions that could affect their participation in the study such as:
 - a. Symptomatic, or history of documented congestive heart failure (NY Heart Association functional classification III-IV).
 - b. Myocardial infarction within 6 months of enrollment.

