10 MEASUREMENT OF EFFECT

During the study period, all subjects will be evaluated for response as per Section 7: Study Assessments and Treatment Schedules. The determination of response and progression will be based on iwCLL criteria (Hallek, et al., 2018). Radiographic and clinical tumor assessments will be performed by the study team/investigator.

All baseline assessments to characterize disease will be performed within 30 days of Cycle 1 Day 1.

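### The qualifying MRD sample may be drawn before the last permitted anti-CD20 dose, so a change that follows that dose can count as a conversion in the primary U-MRD rate

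*Combined protocol and SAP*

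**What the plan says.** **Timing of the baseline sample.** Footnote 7 in Section 7.1 specifies "MRD analysis (central lab) in peripheral blood (PB) performed within 30 days prior to Cycle 1/Day 1". Section 10 agrees: "All baseline assessments to characterize disease will be performed within 30 days of Cycle 1 Day 1". The screening column of the same schedule runs from day -28 to day -1, so the schedule and its footnote differ by two days.

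**Timing of prior anti-CD20.** The Synopsis (Enrollment) says that any therapy given alongside the backbone drug, "including anti-CD20 therapy, must have been discontinued 21 days prior to Day 1 of Cycle 1". Exclusion 1 in Section 4.2 sets the same 21-day limit for other cancer therapy and adds: "This does not include ibrutinib, acalabrutinib or venetoclax but does include anti-CD20 therapy". Both limits are counted from C1D1, not from the MRD sample.

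**What qualifies a subject.** Inclusion 2 in Section 4.1 reads: "Minimal residual disease (MRD) positive (D-MRD) as determined by central lab performed during screening period". It sets no order or interval relative to anti-CD20. Section 4 requires eligibility to hold at screening and again at C1D1, but the schedule marks peripheral blood MRD at screening and not at C1D1.

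**What is counted.** Section 11.6.1.1 counts every subject detectable at baseline who is undetectable on two post-baseline samples at least 4 weeks apart. Sampling starts in Cycle 3. No analysis takes account of recent anti-CD20.

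**The concern.** The trial selects subjects who have not reached U-MRD on their current drug and asks how many do so once ublituximab and umbralisib are added (Section 5.1). There is no concurrent control, and Section 11.1 states no reference rate. The baseline sample is therefore the only evidence that a subject was still MRD-positive when the added drugs began.

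If that sample predates the last dose of another anti-CD20 antibody, it does not describe the subject who starts Cycle 1. A subject who became undetectable after that dose would enter as MRD-positive and could be credited to the study regimen. Time to U-MRD would be affected in the same way. Such subjects are foreseeable: the enrollment text itself refers to anti-CD20 given with the backbone drug, and Section 2.1 names venetoclax with rituximab as an approved regimen.

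**Working it through.** There is no planned figure to reproduce. The Synopsis gives up to about 28 subjects per cohort, and Section 11.1 gives no error rate, power, null rate or target rate.

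**Step 1: order of events.** Inputs are the earliest sample (day -30 by footnote 7, day -28 by the screening column) and the latest permitted anti-CD20 dose (day -21, or day -22 if day -21 itself is read as excluded).

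- Footnote 7: 30 - 21 = 9 days, or 30 - 22 = 8 days.
- Screening column: 28 - 21 = 7 days, or 28 - 22 = 6 days.

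On every reading the baseline can come before the last dose.

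**Step 2: does anything later catch it?** Cycle 3 Day 1 is 56 days after C1D1, so the first post-baseline test is at least 21 + 56 = 77 days (11 weeks) after a day -21 dose. Confirmation follows at 77 + 28 = 105 days (15 weeks) or later. A short-lived effect would probably fail this test. However, by Cycle 3 Day 1 the subject has been scheduled for another anti-CD20: 150 + 750 + 900 + 900 mg of ublituximab in Cycle 1 and 900 mg in Cycle 2, in total 3,600 mg. A subject already undetectable at C1D1 could be held there by study treatment and pass both tests.

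**Step 3: effect on the primary rate.** With k such subjects who would not otherwise have converted, the rate rises by k/28. Exact (Clopper-Pearson) 95% intervals at n = 28, with k assumed:

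| Converters without carry-over | k = 0 | k = 1 | k = 2 | k = 3 |
|---|---|---|---|---|
| 7 | 25.0% (10.7-44.9) | 28.6% (13.2-48.7) | 32.1% (15.9-52.4) | 35.7% (18.6-55.9) |
| 14 | 50.0% (30.6-69.4) | 53.6% (33.9-72.5) | 57.1% (37.2-75.5) | 60.7% (40.6-78.5) |

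This compares the subject counted as a converter with the same subject counted as a failure. If the subject would instead have been screened out, the shift is smaller: 8/28 - 7/27 = 28.6% - 25.9%, about 2.6 points.

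**Step 4: expected size under assumptions.** Let f be the share of subjects exposed to the problem, q the chance that the earlier anti-CD20 alone makes such a subject undetectable, and p the true conversion rate. Expected inflation is f × q × (1 - p).

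- Low: 0.10 × 0.10 × (1 - 0.50) = 0.5 points, or 0.14 subjects of 28.
- High: 0.50 × 0.30 × (1 - 0.25) = 11.25 points, or 3.15 subjects of 28.

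The documents give none of f, q or p. The high end needs half the cohort to be exposed.

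**The case against.** The strongest reply is that the scenario is narrow. A subject must have had anti-CD20 within about a month of C1D1, have been sampled before that dose, and remain undetectable 11 weeks later and again at least 4 weeks after that. This stands as a limit on size. It does not close the gap, because study ublituximab can sustain a result that the earlier antibody produced.

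A second reply is that the primary objective only asks for the U-MRD rate with the combination, with no hypothesis test. That is true, but Section 5.1 frames the question as the effect of the addition, and readers will take the rate that way.

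Two stronger readings are tempting and are not supported:

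- **That earlier anti-CD20 is still lowering MRD at baseline, by an amount its half-life predicts.** The documents give no MRD kinetics after anti-CD20. Section 2.2.2 reports median lymphocyte counts for ublituximab (46.6 at baseline, then 1.5, 1.4 and 2.0 × 10⁹/L at months 1, 4 and 6). That is early depletion followed by a plateau, and lymphocyte count is not MRD. Section 2.2.2.1 notes "Concentration was still measurable in at least one patient of the cohort up to day 169", but that concerns ublituximab only. The tabulated half-life after the eighth infusion is 147.8 h with SD 133.8 in 11 subjects, and the text says half-life fell while the table shows it rising. These data make persistence plausible but do not size it.
- **That entry at 6 months on the backbone inflates the rate in the same way.** Inclusion 1 admits subjects "currently receiving treatment with ibrutinib, acalabrutinib or venetoclax for greater than or equal to 6 months", and some might have converted on that drug alone. This is a general limitation of a single-arm design and a stated choice. No data in the documents show late conversion on the backbone.

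**Conclusion.** The gap is real and follows from the stated windows: a fully compliant subject can have a baseline MRD sample 8 to 9 days (6 to 7 by the screening column) before the last permitted anti-CD20 dose, with no later check before treatment. Any resulting bias in the primary rate is upward, by up to 3.6 points per affected subject at n = 28. The number affected cannot be estimated from the documents, and the Cycle 3 start and the confirmation rule probably keep it small. The conclusion rests on the order of the two windows and the absence of a C1D1 sample, and not on any claim about how long anti-CD20 acts on MRD. It does not invalidate the design. It is a cheap improvement that removes an avoidable ambiguity about the baseline.

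**What to change.** 1. In inclusion 2 and footnote 7, require the qualifying MRD sample to be drawn after the last dose of any prior anti-CD20 therapy and before C1D1 dosing. The washout stays as written. A minimum interval between dose and sample is deliberately not proposed: with central-laboratory turnaround it could in effect lengthen the washout.
2. Reconcile the 30-day window in footnote 7 and Section 10 with the day -28 to -1 screening column.
3. In Section 11.6.1.1, add one supportive U-MRD rate per cohort, with its exact interval, excluding subjects with recent prior anti-CD20. Fix the cut in advance; within 6 months of C1D1 is one example. This is an analysis cut, not an eligibility rule.

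**Cost.** A few subjects are sampled later in screening. The date of the last anti-CD20 dose must be recorded, since exclusion 1 needs only a yes or no at 21 days. The supportive interval is wider: if half a cohort were excluded, 7/14 has an exact 95% interval of about 23% to 77%, against 30.6% to 69.4% for 14/28. The sample size and the primary estimator do not change. Ordering the sample after the dose does not rule out a later effect of that dose, which is why the supportive rate is also needed.
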